### **8.2.10 Compliance (Medication Adherence)**

A day within the study will be considered an On-Therapy day if the subject receives the study medication infusion. The number of Days Should be on Therapy is the total number of days from the first day of study medication to the date of the last dose of study medication. For each subject, percent compliance will then be calculated using the following formula:

$$\text{Percent Compliance} = \frac{\text{Number of Days on Therapy}}{\text{Number of Days Should be on Therapy}} \times 100.$$

Summary statistics will be provided on percent compliance for the FAS population.

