## **5.2 Trial Treatment(s)**

The treatment to be used in this trial is outlined below in [Table 2](#).

Table 2 Trial Treatment

Drug	Dose/Potency	Dose Frequency	Route of Administration	Regimen/Treatment	Use
MK-3475	2 mg/kg	Q3W	IV infusion	Day 1 of each cycle	Experimental

The MK-3475 dosing interval may be increased due to toxicity as described in Section 5.2.1.2.

Trial treatment should begin on the day of randomization or as close as possible to the date on which the subject is allocated/assigned.

The investigator shall take responsibility for and shall take all steps to maintain appropriate records and ensure appropriate supply, storage, handling, distribution and usage of trial treatments in accordance with the protocol and any applicable laws and regulations.

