Pneumonitis	2	Toxicity resolves to Grade 0-1	Toxicity does not resolve within 12 weeks of last dose or inability to reduce corticosteroid to 10 mg or less of prednisone or equivalent per day within 12 weeks
	3-4	Permanently discontinue	Permanently discontinue
Renal Failure or Nephritis	2	Toxicity resolves to Grade 0-1	Toxicity does not resolve within 12 weeks of last dose or inability to reduce corticosteroid to 10 mg or less of prednisone or equivalent per day within 12 weeks
	3-4	Permanently discontinue	Permanently discontinue
All Other Drug-Related Toxicity c	3 or Severe	Toxicity resolves to Grade 0-1	Toxicity does not resolve within 12 weeks of last dose or inability to reduce corticosteroid to 10 mg or less of prednisone or equivalent per day within 12 weeks
	4	Permanently discontinue	Permanently discontinue

Note: Permanently discontinue for any severe or Grade 3 (Grade 2 for pneumonitis) drug-related AE that recurs, or any life-threatening event.

a For patients with liver metastasis who begin treatment with Grade 2 AST or ALT, if AST or ALT increases by greater than or equal to 50% relative to baseline and lasts for at least 1 week then patients should be discontinued.

b If symptoms resolve within one hour of stopping drug infusion, the infusion may be restarted at 50% of the original infusion rate (e.g., from 100 mL/hr to 50 mL/hr). Otherwise dosing will be held until symptoms resolve and the subject should be premedicated for the next scheduled dose; Refer to [Table 4](#) – Infusion Treatment Guidelines for further management details.

c Patients with intolerable or persistent Grade 2 drug-related AE may hold study medication at physician discretion. Permanently discontinue study drug for persistent Grade 2 adverse reactions for which treatment with study drug has been held, that do not recover to Grade 0-1 within 12 weeks of the last dose.

Dosing interruptions are permitted in the case of medical / surgical events or logistical reasons not related to study therapy (e.g., elective surgery, unrelated medical events, patient vacation, and/or holidays). Subjects should be placed back on study therapy within 3 weeks of the scheduled interruption, unless otherwise discussed with the Sponsor. The reason for interruption should be documented in the patient's study record.

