### **5.2.2 Timing of Dose Administration**

MK-3475 should be administered on Day 1 of each cycle as a 30-minute IV infusion (25-40 min) every 3 weeks (Q3W) after all procedures/assessments have been completed as detailed on the Trial Flow Chart (Section 6.0), except for the post-infusion PK sample time points listed in the Trial Flow Chart. Sites should make every effort to target infusion timing to be as close to 30 minutes as possible. MK-3475 may be administered up to 3 days before or after the scheduled Day 1 of each cycle due to administrative reasons only.

All trial treatments will be administered on an outpatient basis. The specific time of trial treatment infusion (e.g., time of the week for first administration; time of the day for each administration) should take into consideration PK sampling time points and study visit procedures.

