
1) In general, assessments/procedures are to be performed on Day 1 and prior to the first dose of treatment for each cycle, and the window for each visit is ± 3 days unless otherwise specified. Treatment cycles are 3 weeks (Q3W); however the treatment cycle interval may be increased due to toxicity according to the dose modification guidelines provided in Section 5.2.1.2. If the interval is increased, all procedures except imaging should be performed based on the new dosing schedule.
 
2) In subjects who discontinue study therapy without documented disease progression, every effort should be made to continue monitoring their disease status by radiologic imaging every 12 weeks (± 1 week) until (1) the start of new anti-cancer treatment, (2) documented disease progression, (3) death, or (4) the end of the study, whichever occurs first.
 
3) After the start of new anti-cancer treatment or documented disease progression, the subject should be contacted by telephone every 12 weeks to assess for survival status.
 
4) Written consent must be obtained prior to performing any protocol specific procedure. Results of a test performed prior to the subject signing consent as part of routine clinical management are acceptable in lieu of a screening test if performed within the specified time frame (e.g., within 4 weeks prior to the first dose of trial treatment). Screening number will be assigned when the study informed consent is signed.
 
5) Prior medications - Record all medications taken within 4 weeks of screening visit. Concomitant medications - Enter new medications started during the trial through the Safety Follow-up visit. Record all medications taken for SAE/ECI s as defined in Section 7.2.
 
6) Record all AEs occurring within 30 days after the last dose of trial treatment. Report all SAEs occurring within 90 days after the last dose of trial treatment or 30 days of the end of treatment if the subject initiates new anticancer therapy, whichever is earlier. Report all ECIs occurring up until 90 days after the last dose of trial treatment or the start of new anti-cancer treatment, whichever comes first. Afterwards, report only SAEs and ECIs that are related to trial treatment. Adverse experiences and laboratory safety measurements will be graded per NCI CTCAE version 4.0. All adverse experiences, whether gradable by CTCAE or not, will also be evaluated for seriousness.
 
7) Perform physical examinations at predose on the day of the study treatment visit. A full physical examination will be performed at screening and every 3 cycles after Cycle 5.
 
8) Vital signs to include temperature, pulse, respiratory rate, weight and blood pressure. If a patient's baseline weight does not fluctuate by more than 10%, this weight can be used to calculate dose. Height will be measured at screening only.
 
9) ECG should be performed within 30 minutes of the end of infusion after dosing for Cycle 1 and Cycle 8, and 30 day post-discontinuation.
 
10) For women of reproductive potential, a urine pregnancy test should be performed within 72 hours prior to first dose of trial treatment. If urine pregnancy results cannot be confirmed as negative, a serum pregnancy test performed by the local study site laboratory will be required. Pregnancy tests (serum and/or urine tests) should be repeated if required by local guidelines.
 
11) Coagulation factors (PT/INR and aPTT) should be tested as part of the screening procedures for all subjects. Any subject receiving anticoagulant therapy should have coagulation factors monitored closely throughout the trial.
 
12) Laboratory tests for screening are to be performed locally within 10 days prior to the first dose of trial treatment. After Cycle 1, lab samples can be collected up to 72 hours prior to the scheduled time point. Following Cycle 6, urinalysis should be performed every 6 cycles and FT3, FT4 and TSH should be performed every 2 cycles. See Section 7.1.3 for details regarding laboratory tests.
 
13) Unresolved abnormal labs that are drug related AEs should be followed until resolution. Labs do not need to be repeated after the end of treatment if labs are within normal range.
 
14) KL-6 and β-D glucan will be measured for pulmonary evaluation at screening (within 10 days prior to the first dose of study treatment) and thereafter if a subject develops suspected pneumonitis, an additional test may be performed at the discretion of the investigator.
														

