### **8.2.9 Interim Analyses**

No efficacy interim analyses are planned in this trial.

The analysis conducted at the time when all patients are enrolled and have either discontinued or have at least 24 weeks of follow-up since first dose is the main analysis time, if more than 7 /28 responses observed at that time, the trial will declare positive and team will prepare for filing. After the main analysis, the study still follows patients for a longer period of time for duration of response and OS.

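### The percent-compliance formula in 8.2.10 divides infusion days by calendar days, so perfect 3-weekly dosing scores 9.1% after two doses, 5.3% at week 24 and 4.9% at 24 months

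*Combined protocol and SAP*

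**What the plan says.** Section 8.2.10 builds the statistic from two counts. For the numerator: "A day within the study will be considered an On-Therapy day if the subject receives the study medication infusion". For the denominator: "The number of Days Should be on Therapy is the total number of days from the first day of study medication", running to the date of the last dose. Percent compliance is the first count divided by the second, times 100. The section then commits to reporting it: "Summary statistics will be provided on percent compliance for the FAS population".

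Table 2 in section 5.2 gives the regimen as a single infusion on "Day 1 of each cycle", and section 5.2.2 sets the cycle at 3 weeks with a window of 3 days either side.

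Two other sections touch on dosing, and neither alters the formula. Section 7.1.1.9 compares the volume infused with the volume prepared at each dose. Section 8.2.11 counts the cycles in which an infusion was given, without a denominator. Nothing in the documents treats the whole 3-week cycle as time on therapy, or restricts the denominator to days on which an infusion was due.

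**The concern.** The two counts are in different units. One is infusions and the other is calendar days, which suits a daily medicine but not a 3-weekly infusion. With two or more doses, full adherence cannot come near 100%.

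The error also depends on how long the subject was treated. The main analysis takes place when all subjects "have either discontinued or have at least 24 weeks of follow-up since first dose is the main analysis time", so it will mix short and long courses. A summary over that mix partly reflects treatment length. Read literally, the denominator also takes in every day of a dose hold and, for a retreated subject, the off-treatment gap before the Second Course Phase. Both lower the score further.

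What is at stake is limited: one reported descriptive statistic for the FAS that cannot be read as adherence.

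**Working it through.** The plan states no compliance percentage, so there is no figure of its own to reproduce. The check applies the formula as written to perfect dosing.

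**Inputs**
- One infusion every 21 days (sections 5.2 and 5.2.2).
- Cycle 8 is week 21 in the flow chart (section 6.1), so Cycle 9 is week 24, the follow-up used for the main analysis in section 8.2.9.
- Treatment for up to 24 months from first dose (section 5.8). At 21-day spacing the last on-schedule dose in that period is dose 35, at week 102.

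**Formula.** For k on-time infusions, counting both end days, the denominator is 21(k − 1) + 1 and the score is 100 × k / [21(k − 1) + 1].

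| On-time doses | Days, first to last | Score | Days ÷ doses (factor too low) |
|---|---|---|---|
| 1 | 1 | 100% | 1 |
| 2 | 22 | 9.1% | 11 |
| 8 | 148 | 5.4% | 18.5 |
| 9 (week 24) | 169 | 5.3% | 18.8 |
| 35 (about 24 months) | 715 | 4.9% | 20.4 |
| limit | – | 1/21 = 4.8% | 21 |

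The subject is fully adherent in every row.

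**Sensitivity to the day count.** As a difference of dates the denominator is 21(k − 1). The scores are then 2/21 = 9.5%, 9/168 = 5.4% and 35/714 = 4.9%, and one dose gives 1/0, which is undefined. If the last dose falls 3 days early or late (inclusive count), the ranges are 8.0 to 10.5%, 5.2 to 5.4% and 4.87 to 4.92%.

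**Can a multiplier rescue it?** Multiplying by 21 gives 42/22 = 191% at two doses, 189/169 = 112% at nine and 735/715 = 103% at 35. It cannot.

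**Missed dose against course length**
- One interior dose missed out of nine: 8/169 = 4.73%, a fall of 5.33 − 4.73 = 0.59 points (before rounding).
- Stopping after two on-time doses instead of nine: 9.09 − 5.33 = 3.77 points higher (before rounding), about 6.4 times as large.
- Stopping after four: 4/64 = 6.25%, 0.92 points higher.
- Stopping after five: 5/85 = 5.88%, 0.56 points higher, about the same size as one missed dose.

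**Illustrative mean (assumed mix).** With 34 subjects at nine on-time doses and one one-dose subject scoring 100%, the mean is (34 × 5.325 + 100)/35 = 8.0%, against 5.3% without that subject.

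**The case against.** The formula itself is hard to defend. The better objections concern how much it matters and how the examples are chosen.

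- **Two doses against nine is an extreme contrast.** This stands in part. Course length outweighs a single missed dose only for subjects who stop after four or fewer doses. At five doses the two effects are about equal, and from 8 to 35 doses the score drifts only from 5.4% to 4.9%.
- **The 8.0% mean is contrived.** It needs inclusive day counting and a one-dose subject who is in the FAS. Under the section 8.1.1 definition, a subject with no post-baseline scan who stopped for a reason other than progression or a drug-related AE would be outside the FAS. Section 8.2.4.1 requires only a dose and baseline data. The mean shows what can happen and is not a forecast.
- **Calling eight of nine doses 89% adherent presumes a rule that the plan does not give.** This is fair. In the data that 8.2.10 uses, a skipped dose and a 3-week delay look identical. The 89% holds if the skipped dose counts as scheduled and not given.
- **The Second Course gap is peripheral.** It is, at the main analysis time, because entry needs a long first course followed by progression.
- **Little is lost, since witnessed dosing, volume checks and cycles infused are recorded anyway, and a figure near 5% would look odd to any reader.** This supports a low grade. It does not make the printed formula right. Following it reports about 5% for perfect dosing, and quietly replacing it is an undocumented departure from the plan.

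**Conclusion.** The concern holds as a minor error. The formula is wrong as written, not merely short of detail. Followed exactly, it understates full adherence by a factor of 11 at two doses and about 19 to 20 from week 24 onward, and it gives 100% or no value at one dose. This rests only on the 3-week schedule and the section's own definitions, and neither day-counting convention nor the dosing window changes it. The direction is right, since more infusions in a fixed period raise the score, but the scale is wrong and varies with treatment length. The effect is confined to one descriptive summary in a single-arm trial. The ORR test and its power, the analysis populations, the safety analyses and extent of exposure are untouched.

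**What to change.** In section 8.2.10, replace the formula with 100 × (infusions received) / (infusions scheduled from first to last dose), calculated separately for the initial Treatment Phase and the Second Course Phase. Subjects dosed on time then score 2/2, 9/9 and 35/35 = 100%.

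Add one sentence saying whether cycles delayed under the protocol's own hold and interruption rules count as scheduled. It is needed because footnote 1 of the section 6.1 flow chart moves the schedule with the dose: "If the interval is increased, all procedures except imaging should be performed based on the new dosing schedule". Section 5.2.1.2 also allows interruptions for reasons unrelated to study therapy: "Subjects should be placed back on study therapy within 3 weeks of the scheduled interruption, unless otherwise discussed with the Sponsor". Take eight doses with one 3-week delay, that is six intervals of 21 days and one of 42, spanning 6 × 21 + 42 + 1 = 169 days. The new formula gives 8/8 = 100% if the schedule moves and 8/9 = 89% if the delayed cycle counts. Under the first reading most subjects will sit near 100%, and the report should say so.

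The cost is one formula and one sentence. The current formula already needs infusion days and first and last dose dates, and section 8.2.11 already counts cycles with an infusion. No dose, hold or stopping rule changes.

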### **8.2.11 Extent of Exposure**

Extent of Exposure for a subject is defined as number of cycles in which the subject receives the study medication infusion. Summary statistics will be provided on Extent of Exposure for APaT population.

## **9.0 LABELING, PACKAGING, STORAGE AND RETURN OF CLINICAL SUPPLIES**

### **9.1 Investigational Product**

The investigator shall take responsibility for and shall take all steps to maintain appropriate records and ensure appropriate supply, storage, handling, distribution and usage of investigational product in accordance with the protocol and any applicable laws and regulations.

Clinical Supplies will be provided by the Sponsor as summarized in Table 10.

After the time of the marketing approval of MK-3475, “clinical trial drug” of MK-3475 will be replaced with “post-marketing clinical trial drug”. The subjects can receive treatment of MK-3475 as post-marketing clinical trial drug.

Table 10 Product Descriptions

Product Name & Potency	Dosage Form
MK-3475 100 mg/ 4mL	Solution for Injection

### **9.2 Packaging and Labeling Information**

Clinical supplies will be affixed with a clinical label in accordance with regulatory requirements.

Subjects will receive open label vials every 3 weeks (Q3W). Each kit will contain 1 vial.

### **9.3 Clinical Supplies Disclosure**

This trial is open-label; therefore, the subject, the trial site personnel, the Sponsor and/or designee are not blinded. Treatment (name, strength or potency) is included in the label text; random code/disclosure envelopes or lists are not provided.

### **9.4 Storage and Handling Requirements**

Clinical supplies must be stored in a secure, limited-access location under the storage conditions specified on the label.

Receipt and dispensing of trial medication must be recorded by an authorized person at the trial site.

Clinical supplies may not be used for any purpose other than that stated in the protocol.

## **9.5 Returns and Reconciliation**

The investigator is responsible for keeping accurate records of the clinical supplies received from the Sponsor or designee, the amount dispensed to and returned by the subjects and the amount remaining at the conclusion of the trial.

For all trial sites, the local country Sponsor personnel or designee will provide appropriate documentation that must be completed for drug accountability and return.

# **10.0 ADMINISTRATIVE AND REGULATORY DETAILS**

## **10.1 Confidentiality**

### **10.1.1 Confidentiality of Data**

By signing this protocol, the investigator affirms to the Sponsor that information furnished to the investigator by the Sponsor will be maintained in confidence, and such information will be divulged to the institutional review board, ethics review committee (IRB/ERC) or similar or expert committee; affiliated institution and employees, only under an appropriate understanding of confidentiality with such board or committee, affiliated institution and employees. Data generated by this trial will be considered confidential by the investigator, except to the extent that it is included in a publication as provided in the Publications section of this protocol.

### **10.1.2 Confidentiality of Subject Records**

By signing this protocol, the investigator agrees that the Sponsor (or Sponsor representative), IRB/ERC, or regulatory authority representatives may consult and/or copy trial documents in order to verify worksheet/case report form data. By signing the consent form, the subject agrees to this process. If trial documents will be photocopied during the process of verifying worksheet/case report form information, the subject will be identified by unique code only; full names/initials will be masked prior to transmission to the Sponsor.

By signing this protocol, the investigator agrees to treat all subject data used and disclosed in connection with this trial in accordance with all applicable privacy laws, rules and regulations.

### **10.1.3 Confidentiality of Investigator Information**

By signing this protocol, the investigator recognizes that certain personal identifying information with respect to the investigator, and all subinvestigators and trial site personnel, may be used and disclosed for trial management purposes, as part of a regulatory submissions, and as required by law. This information may include:

1. name, address, telephone number and e-mail address;
2. hospital or clinic address and telephone number;

3. curriculum vitae or other summary of qualifications and credentials; and
4. other professional documentation.

Consistent with the purposes described above, this information may be transmitted to the Sponsor, and subsidiaries, affiliates and agents of the Sponsor, in your country and other countries, including countries that do not have laws protecting such information. Additionally, the investigator's name and business contact information may be included when reporting certain serious adverse events to regulatory authorities or to other investigators. By signing this protocol, the investigator expressly consents to these uses and disclosures.

If this is a multicenter trial, in order to facilitate contact between investigators, the Sponsor may share an investigator's name and contact information with other participating investigators upon request.

#### **10.1.4 Confidentiality of IRB/IEC Information**

The Sponsor is required to record the name and address of each IRB/IEC member that reviews and approves this trial. The Sponsor is also required to document that each IRB/IEC meets regulatory and ICH GCP requirements by requesting and maintaining records of the names and qualifications of the IRB/IEC members and to make these records available for regulatory agency review upon request by those agencies.

### **10.2 Compliance with Financial Disclosure Requirements**

Financial Disclosure requirements are outlined in the US Food and Drug Administration Regulations, Financial Disclosure by Clinical Investigators (21 CFR Part 54). It is the Sponsor's responsibility to determine, based on these regulations, whether a request for Financial Disclosure information is required. It is the investigator's/subinvestigator's responsibility to comply with any such request.

The investigator/subinvestigator(s) agree, if requested by the Sponsor in accordance with 21 CFR Part 54, to provide his/her financial interests in and/or arrangements with the Sponsor to allow for the submission of complete and accurate certification and disclosure statements. The investigator/subinvestigator(s) further agree to provide this information on a Certification/Disclosure Form, commonly known as a financial disclosure form, provided by the Sponsor or through a secure password-protected electronic portal provided by the Sponsor. The investigator/subinvestigator(s) also consent to the transmission of this information to the Sponsor in the United States for these purposes. This may involve the transmission of information to countries that do not have laws protecting personal data.

